## INTRODUCTION

Dementia is one of the main causes of disability and dependency among older adults worldwide, constituting a public health priority due to its significant human and financial costs to society (WHO, 2017). Aside from cognitive decline, dementia progression leads to the appearance of at least one behavioral or psychological symptom of dementia (BPSD) in the majority of the individuals at some point during their disease (Lyketsos et al., 2000; Steinberg et al., 2008). Pharmacological and non-pharmacological interventions have been proposed for the treatment of both BPSD and cognitive impairment. Numerous guidelines and expert recommendations initially recommend the use of non-pharmacological strategies to manage dementia due to the absence of adverse events (Dyer et al., 2018).

Nonpharmacological interventions in dementia include bright light therapy (BLT). This therapy consists of the controlled application of certain levels of light that can be administered in different ways, such as outdoor sunlight, light boxes, light visors worn on the head, ceiling lights, or the dawn-dusk simulation (Forbes et al., 2014). There is some evidence that effective doses of light would stimulate circadian cycles, thus affecting sleep efficiency, depression or behavioral problems in older adults with dementia (van Maanen et al., 2016; Sloane et al., 2008; Abraha et al., 2017). Of note is the great methodological heterogeneity among the studies with respect to light intensity, frequency, interval, time of day and total duration of the intervention program (Forbes et al., 2014). The lack of consensus on the protocol for BLT application, as well as the existence of little research in person with advanced stages of dementia, calls for further research to explore in depth the immediate, short- and long-term effects of BLT in this population.

## OBJECTIVES

To study the short- and long-term effects of bright light therapy on mood, behavior, sleep and cognition in a sample of institutionalized older adults with moderate to very severe dementia.

To explore the immediate effects of bright light therapy sessions on behavior, mood and physiological parameter in a sample of institutionalized older adults with moderate to very severe dementia.

To compare the effectiveness of bright light therapy sessions with other non-pharmacological interventions in people with dementia.

## MATERIAL AND METHODS

### Study design

This longitudinal, comparative and prospective study conducted between October 2018 and April 2019, is a 2 x 2 randomized controlled trial using a two-group design (BLT vs. control) and two repeated measures (pre- vs. postintervention). In addition, the behavior, mood and physiological parameters of the BLT group participants were assessed immediately before, after and during each session.

This study is performed following the CONSORT (CONsolidated Standards of Reporting Trials) 2010 guideline.

## Study setting and participants

Participants were recruited between September and October 2018 among residents of the Gerontological Complex La Milagrosa (A Coruña, Spain).

Inclusion criteria: (a) age 65 years or older, (b) diagnosis of dementia, and (c) a score  $\geq 4$  points on the Global Deterioration Scale (GDS; Reisberg et al., 1982), ranging from moderate to very severe cognitive decline.

Exclusion criteria: (a) high ocular sensitivity to light (photosensitivity), (b) preexisting ocular abnormalities, or (c) having any severe ocular disorder that did not allow them to open their eyes or that implied a very low visual acuity.

39 participants will be recruited, stratified according to their cognitive status and subsequently randomly placed into two groups: the BLT group (=19) and the control group (n=20).

## Intervention

### Light therapy lamps

For the development of the intervention it was necessary to purchase two light therapy lamps (Beurer TL 100 daylight lamps). These devices (Fig. 1 and Fig. 2) are specially designed for bright light therapy, providing the required uniform illumination with an intensity of up to 10,000 lux.

Figure 1. Lamp Beurer TL 100

Figure 2. Light therapy lamps in the intervention room

### Intervention

BLT sessions were carried out in a quiet room of the Gerontological Complex especially enabled for their proper development and were implemented by a research psychologist specialized in Gerontology. The devices used for the intervention were bright white light lamps providing an intensity of 10,000 lux. Four users participated in each session, placing two users per lamp, seated in a comfortable chair with armrests 70 cm from the lamp. The sessions were 30 minutes/day in the time slot between 10:30 and 12:00 in the morning, 5 days a week (Monday to Friday) for 4 weeks (total 20 sessions). Two groups of participants per day were established, the first shift being from 10:30 to 11:00, and the second from 11:15 to 11:45 a.m., which means the stimulation of 8 people per day (month). During the sessions, while exposed to light, participants were watching documentaries on neutral topics (nature, Spanish and Galician culture, etc.). Each session lasted 30 minutes, unless the participant expressed the desire to

leave the room and could not be convinced to remain in it without generating agitation. Participants who responded negatively to light exposure were immediately withdrawn from the intervention. Only those sessions in which the person remained at least 80% of the expected time ( $\geq 22.5$  minutes) were considered as sessions performed. Additionally it is established as a final criterion to consider the participant to complete at least 80% of the scheduled sessions (16 out of 20 sessions).

In every session, the researchers supervised the users to ensure full compliance with the treatment and recorded the physiological parameters (heart rate and blood oxygen saturation) as well as the mood and behavior of the participants.

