## Measures

Pre- and post-intervention assessments were performed on all subjects in the sample (control and experimental group). Pre-intervention data were collected during the week before the start of the intervention, and post-intervention data were recorded during the week after the end of the intervention. Additionally, data on physiological parameters, mood, and behavior were recorded in each session for the participants of the experimental group.

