### **Data management and statistical analysis**

The data of the participants are coded/pseudo-anonymized to ensure confidentiality and users' privacy for research use. Identifiable information is coded with artificial identifiers. The documentation to re-identify the participants will be only available to a medical doctor that collaborates with the research group, ensuring privacy during all data exploitation and dissemination (conferences, Ph.D. thesis, and scientific articles).

The general description of the population studied is performed by univariate analysis. The distribution in the study groups of sociodemographic factors (gender, age, level of education) was evaluated with Student's t test (or Mann-Whitney U test if the assumption of normality is not met or if the sample size is not large enough) for continuous variables and Pearson's Chi-square test for categorical variables. The normal distribution of the variables is tested using the Sapiro-Wilk test. For subsequent analyzes, parametric or non-parametric tests were applied depending on whether the assumption of normality was met or not for each measured variable. Two-way analysis of variance (ANOVA) is used to determine the existence of differences in agitation, behavior, anxiety, cognitive status or severity of dementia at two points in time (pre-vs. post-). Intrasubject variables were considered as intrasubject variables, these measures over time, and intersubject variables were the study group (control or experimental). The differences between the groups are tested by means of the group-tempo interaction. Sphericity assumptions are determined by Mauchly's sphericity test. In case of sphericity transgression, the Pillai trace test or the univariate F-test adjusted to epsilon (Greenhouse-Geisser) (Geisser and Greenhouse, 1958) is performed.

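### The 16-of-20-session criterion can act as a post-randomisation exclusion in the BLT arm only, and no as-randomised analysis set is named

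*SAP*

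**What the plan says.** Under Study setting and participants, 39 people are stratified by cognitive status and "randomly placed into two groups: the BLT group (=19) and the control group (n=20").

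Under Intervention, the BLT programme runs "5 days a week (Monday to Friday) for 4 weeks (total 20 sessions"). A minimum-time rule first decides whether a session counts as performed. The SAP then adds: "it is established as a final criterion to consider the participant to complete at least 80% of the scheduled sessions", which it gives as 16 of 20. This is the only rule in the document on which randomised participants are considered.

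The same section gives two ways of falling short. "Participants who responded negatively to light exposure were immediately withdrawn from the intervention". A session may also end early if the person wishes to "leave the room and could not be convinced to remain in it without generating agitation".

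Under Measures, "Pre- and post-intervention assessments were performed on all subjects in the sample (control and experimental group"). Per-session data are recorded for the experimental group only.

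Under Data management and statistical analysis, agitation, behaviour, anxiety, cognitive status and dementia severity are analysed by two-way ANOVA, and "The differences between the groups are tested by means of the group-tempo interaction". No analysis population is named for this test or any other.

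**The concern.** The attendance criterion comes directly after a rule that discards sessions failing their own threshold. Read in parallel, a participant who fails the second rule is not considered either. If that governs the between-group test, participants are removed after randomisation, from one arm only, for reasons that can be related to what is measured. No control can be removed for a comparable reason, so the arms are no longer the groups that randomisation created.

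The direction depends on why people fall short:

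- If failure tracks a worse change or a worse post-intervention score, the remaining BLT participants look better than the full arm and the bias favours BLT.
- If failure is unrelated to change, there is no bias.
- If failure tracks the measured baseline score, the bias runs against BLT.

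The SAP gives no means of telling which applies. Leaving the set unnamed also allows it to be chosen once results are known.

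**Working it through.** **The plan's own figure.** 5 days × 4 weeks = 20 sessions, and 0.80 × 20 = 16. The threshold reproduces exactly. The SAP contains no sample-size or dropout calculation to check.

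**Who can fail.** BLT: up to 19. Control: 0 of 20, since no control sessions are described.

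**Inputs for the size of the bias.** From the SAP: 19 v 20 participants and a significance level of 0.05. Assumed, because the SAP does not give them: a two-sided test, k (the number of BLT participants failing), r (the correlation between failure and outcome), and a pre–post correlation of 0.7.

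**Method.** 40,000 trials were simulated per scenario with no true effect. The k of 19 BLT participants with the highest intolerance score were dropped, and no control was dropped. The test was a t-test on change scores, which is equivalent to the group-by-time interaction with two groups and two time points. Bias is in SD of the change score; positive favours BLT.

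*Failure correlated r with a worse change score:*

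| k dropped | Bias, r = 0.3 / 0.5 / 0.7 | Type I error, r = 0.3 / 0.5 / 0.7 |
|---|---|---|
| 1 | 0.033 / 0.052 / 0.074 | 5.2% / 5.3% / 5.9% |
| 3 | 0.081 / 0.133 / 0.190 | 5.5% / 7.1% / 9.6% |
| 5 | 0.128 / 0.212 / 0.294 | 6.6% / 9.4% / 14.1% |

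A separate run with k = 2, 4 and 6 fits this pattern. For r from 0.3 to 0.7 the bias is 0.06–0.13, 0.11–0.24 and 0.15–0.35 SD, with type I error 5.3–7.5%, 6.0–11.6% and 6.8–17.4%. In that run, analysing all 39 as randomised held type I error at 4.8–5.1%.

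**Hand check of the largest cell in the table.** With k = 5 the comparison is 14 v 20. The standard error is √(1/14 + 1/20) = 0.348 SD, so the shift is 0.294 / 0.348 = 0.84 standard errors. By the normal approximation, P(Z > 1.96 − 0.84) + P(Z < −1.96 − 0.84) is about 13.5%, close to the simulated 14.1%.

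*Other mechanisms:*

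| Failure tracks | k = 1, r = 0.3 / 0.5 / 0.7 | k = 3 | k = 5 |
|---|---|---|---|
| Post score | +0.011 / +0.019 / +0.029 | +0.032 / +0.052 / +0.074 | +0.048 / +0.081 / +0.113 |
| Measured baseline | −0.011 / −0.020 / −0.028 | −0.030 / −0.054 / −0.073 | −0.046 / −0.083 / −0.116 |

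With r = 0 the bias is within 0.003 of zero and type I error is 4.8–5.1%. When failure tracks the stable symptom level (r = 0.5), the bias is within 0.002 of zero and type I error is 5.0%.

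The second table follows from the first. With a pre–post correlation of 0.7, change correlates with the post score at (1 − 0.7)/√(2 × (1 − 0.7)) = 0.387, and with baseline at −0.387. For k = 5 and r = 0.7, 0.387 × 0.294 = 0.114, against simulated values of 0.113 and −0.116.

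**A related inconsistency.** The rule for a performed session equates 80% of the expected time with 22.5 minutes. But 0.80 × 30 = 24 minutes, and 22.5 / 30 = 75%. The concern does not rest on this, but it leaves unclear which sessions count towards the 16.

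**The case against.** The SAP does not state that anyone is excluded from the between-group test. The sentence sits in the Intervention section and could define who has completed the programme. It could also be an entry rule for the analyses within the BLT arm, such as the week 1 v week 4 comparison and the Friedman test on Interact scores. Used only there, it would not touch the group-by-time contrast. Those who react badly are withdrawn from the intervention, not from the study, and assessments are said to cover all subjects in both groups, which points away from exclusion.

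The bias figures rest on assumed inputs. The largest effects need several failures strongly tied to worsening. Agitation during sessions could equally reflect a stable trait or baseline severity, for which the bias is nil or runs against BLT. The SAP also describes the intervention and assessments largely in the past tense, so new wording may not restore prespecification.

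Much of this stands as a limit on certainty. The wording is ambiguous, the figures show possible rather than likely harm, and a choice of set after seeing the data is a possibility, not something shown. It does not remove the point. Neither alternative reading is confirmed anywhere, and the statement about all subjects concerns data collection, not analysis. Under every reading, the SAP fails to say who enters the group-by-time test.

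**Conclusion.** The concern holds and should be fixed, with medium confidence because of the ambiguous wording. The SAP states a participation criterion that only one arm can fail, for reasons that can be related to its outcomes, and names no as-randomised analysis. Applied as it most naturally reads, the criterion breaks the randomised comparison.

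The size cannot be fixed from the document. Dropping one participant makes little difference. Dropping three to five, with failure moderately to strongly tied to worsening, could add 0.08–0.29 SD in favour of BLT and take a nominal 5% test to between 5.5% and 14.1%. These figures depend on the assumed number failing and correlation; the direction depends on the mechanism, which the SAP does not reveal.

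**What to change.** State under Data management and statistical analysis that the main between-group analysis includes every randomised participant in the allocated arm, whatever the number of sessions attended, using the pre- and post-intervention assessments described under Measures. Say there how a missing post-intervention assessment is handled.

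Reword the 16-of-20 sentence to say what it governs, and keep that set as a labelled per-protocol sensitivity analysis. Report how many BLT participants fell below 16 sessions, with reasons, and any other exclusions by arm. If results have already been produced, say which set was used. The 80% and 22.5-minute figures in the session rule must also be reconciled, because they determine who reaches 16.

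The cost is SAP wording and one extra run of the same models. No new data are needed, provided that all 39 were in fact assessed, as Measures indicates. The downside is that the estimate may be less favourable to BLT once poorly adherent participants are included.

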## Measures

Pre- and post-intervention assessments were performed on all subjects in the sample (control and experimental group). Pre-intervention data were collected during the week before the start of the intervention, and post-intervention data were recorded during the week after the end of the intervention. Additionally, data on physiological parameters, mood, and behavior were recorded in each session for the participants of the experimental group.

### Socio-demographic variables

Age (years), gender, and educational level.

### Mini-Mental State Examination (MMSE)

Cognitive evaluation: brief screening test for cognitive impairment.

### Severe Mini-Mental State Examintation (SMMSE)

Cognitive evaluation: brief assessment of severe cognitive impairment in advanced stages of dementia. This test was applied only to individuals who obtained a score of 10 points or less in the MMSE.

### Cambridge Cognitive Examination (CAMCOG)

Cognitive evaluation: more comprehensive cognitive assessment of participants with moderate cognitive impairment (GDS = 4). This scale includes the evaluation of the following domains: orientation, language, memory, attention and calculation, praxis, abstraction, perception and executive function.

### Severe Cognitive Impairment Profile (SCIP)

Cognitive evaluation: a more comprehensive cognitive assessment of participants with moderate-severe to very severe cognitive impairment (GDS = 5, 6 and 7). This scale allows obtaining a performance profile in each of the cognitive domains evaluated (comportment, attention, language, memory, motor, conceptualization, arithmetic, and visuospatial) and calculating a total score indicative of the degree of cognitive impairment: moderately severe, severe, very severe and profound.

### Cornell Scale for Depression in Dementia

Mood evaluation: assessment of signs and symptoms of major depression in patients with dementia focusing on the week preceding the interview. The Cornell Scale utilizes two semi-structured comprehensive interviews that elicits information from the patient and the informant. In those cases in which the patient is not able to respond due to the level of cognitive impairment, information is obtained only from the interview with the informant.

Neuropsychiatric Inventory Questionnaire (NPI-Q)

Mood and behavior evaluation: a brief retrospective (1 month) caregiver self-administered questionnaire for the assessment of 12 neuropsychiatric symptoms: delusions, hallucinations, agitation/aggression, dysphoria/depression, anxiety, euphoria/elation, apathy/indifference, disinhibition, irritability/lability, aberrant motor behaviors, nighttime behavioral disturbances, and appetite/eating disturbances.

Cohen-Mansfield Agitation Inventory (CMAI)

Mood and behavior evaluation: a caregiver rating questionnaire for the assessment of the frequency of manifestations of agitated behaviors. Ratings refer to the two weeks prior to its administration.

Rating for Anxiety in Dementia (RAID)

Mood and behavior evaluation: a clinical rating scale to evaluate severity of anxiety including somatic symptoms and specific fears. Scoring should be based on the two weeks prior to the caregiver interview.

Sleep Disorders Inventory (SDI)

Sleep evaluation: this inventory is an expanded version of one item of the Neuropsychiatric Inventory (NPI). It records the frequency, severity, and caregiver burden of sleep-disturbed behaviors for the two weeks prior to its administration.

Actiwatch AW4 - Actigraphy

Sleep evaluation: actigraphy is a non-invasive method of monitoring circadian rhythm. Actiwatches are worn on the non-dominant wrist of the participants and record movements that are used to estimate sleep parameters with specialized algorithms in computer software programs. Both experimental and control group participants wore the actiwach for 5 days before and 5 days after the intervention.

Among the parameters obtained from actigraphy records, the following were chosen for analysis in the present study: sleep latency, sleep efficiency and total sleep

Figure 3. Actiwatch AW4

Bedford Alzheimer Nursing Severity Scale (BANS-S)

Functional evaluation: a nursing-staff administered questionnaire for the assessment of disease severity in advanced stages of dementia. The questionnaire comprises 7 items: dressing, sleep-wake cycle disturbances, speech, eating, ambulating, muscle rigidity and eye contact.

### Interact scale

Mood and behavior evaluation: the Interact Scale, and its shortened version, named Interact short, were used for the evaluation of immediate effects in the experimental group. Both allows the assessment of changes on mood and behavior, the Interact scale during the sessions, and the Interact short scale in the 10 minutes immediately preceding and in the 10 minutes immediately following the session.

### Pulse oximeter

Physiological parameters evaluation: the heart rate and blood oxygen saturation of the participants in the experimental group were recorded at the beginning and end of each session using a mobile finger pulse oximeter

### **Ethics**

The participants and their legal guardians were informed about the study and they signed the corresponding informed consent. All the information was transmitted adapted to the level of comprehension of the participants in order to facilitate their understanding and comfort throughout the study. The present research protocol (code 2017/408) had the favorable authorization from the Galician Research Ethics Committee of Xunta de Galicia (Spain) and was developed in accordance with the Declaration of Helsinki.

### **Data management and statistical analysis**

The data of the participants are coded/pseudo-anonymized to ensure confidentiality and users' privacy for research use. Identifiable information is coded with artificial identifiers. The documentation to re-identify the participants will be only available to a medical doctor that collaborates with the research group, ensuring privacy during all data exploitation and dissemination (conferences, Ph.D. thesis, and scientific articles).

The general description of the population studied is performed by univariate analysis. The distribution in the study groups of sociodemographic factors (gender, age, level of education) was evaluated with Student's t test (or Mann-Whitney U test if the assumption of normality is not met or if the sample size is not large enough) for continuous variables and Pearson's Chi-square test for categorical variables. The normal distribution of the variables is tested using the Sapiro-Wilk test. For subsequent analyzes, parametric or non-parametric tests were applied depending on whether the assumption of normality was met or not for each measured variable. Two-way analysis of variance (ANOVA) is used to determine the existence of differences in agitation, behavior, anxiety, cognitive status or severity of dementia at two points in time (pre-vs. post-). Intrasubject variables were considered as intrasubject variables, these measures over time, and intersubject variables were the study group (control or experimental). The differences between the groups are tested by means of the group-tempo interaction. Sphericity assumptions are determined by Mauchly's sphericity test. In case of sphericity transgression, the Pillai trace test or the univariate F-test adjusted to epsilon (Greenhouse-Geisser) (Geisser and Greenhouse, 1958) is performed.

The Wilcoxon signed-rank test or the Paired t test are employed to measure significant changes between the Interact short scores from before to after the intervention sessions for each of the assessed mood and behavior items. Likewise, these same tests are used to analyze the evolution of the Interact during scores, comparing the average scores of the first week with those of the fourth week. In addition, the evolution of mood and behavior scores throughout the four weeks of treatment is analyzed with the Friedman test for related samples. The Paired t test is also used to determine the existence of any differences from before to after the sessions in physiological parameters. In the variables in which statistically significant differences are found, Cohen's  $d$  or  $r$  values are used to report the effect size (ES) of these changes. The interpretation of the importance of the ES is made according to the benchmarks defined by Cohen, as follows: small ES ( $d = 0.2$  or  $r = 0.1$ ), medium ES ( $d = 0.5$  or  $r = 0.3$ ), and large ES ( $d = 0.8$  or  $r = 0.5$ ).

The significance threshold is set at a p-value of less than 0.05. All data analysis are performed with the statistical programs SPSS (version 25.0), RStudio software package (Version 1.3.1093) and JAMOVI (The jamovi project, 2020, Version 1.2).

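### The normality rule for choosing tests leaves the randomised pre/post comparison without a defined test when a scale fails it, and it checks raw scores rather than change or residuals

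*SAP*

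**What the plan says.** All of this stands in the SAP under Data management and statistical analysis unless stated otherwise.

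- Normality check: "The normal distribution of the variables is tested using the Sapiro-Wilk test". Change scores and model residuals are not mentioned.
- Selection rule for the analyses that follow: "parametric or non-parametric tests were applied depending on whether the assumption of normality was met or not for each measured variable".
- Pre/post scales: a two-way ANOVA is used for "differences in agitation, behavior, anxiety, cognitive status or severity of dementia at two points in time (pre-vs. post", and "The differences between the groups are tested by means of the group-tempo interaction". Neither statement is conditional on the normality result.
- Mann-Whitney U appears once, for comparing sociodemographic factors between groups: "Student's t test (or Mann-Whitney U test if the assumption of normality is not met or if the sample size is not large enough".
- Wilcoxon signed-rank appears for the Interact scores: "The Wilcoxon signed-rank test or the Paired t test are employed to measure significant changes between the Interact short scores", and again for week 1 against week 4 of the scores taken during sessions.
- Friedman appears for the course of mood and behavior "throughout the four weeks of treatment is analyzed with the Friedman test for related samples".

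The Interact scale section says these scores are collected in the experimental group only. Study setting and participants gives arms of 19 and 20, randomised after stratification by cognitive status.

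**The concern.** The rule has two branches, but only the parametric one contains a test of the randomised comparison. A scale that fails Shapiro-Wilk is sent by the rule to a non-parametric test that the SAP does not name for this purpose, while the next sentences say that the ANOVA is used regardless. An analyst holding the data could follow either statement.

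The rule also looks at the wrong distribution. The interaction with two visits depends on the distribution of change (equivalently, the residuals), and raw scores can be clearly skewed while change is close to symmetric. Bounded symptom scales such as those listed under Measures can plausibly be skewed or floored, so the undefined branch may apply to much of the outcome set.

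At stake is whether the between-group result for those scales comes from a test fixed in advance. If the gap were filled with before/after tests inside each arm, a change common to both arms could be read as a treatment effect.

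**Working it through.** The SAP states no SD, effect size or power for these outcomes, so there is no figure of its own to reproduce. Its inputs are arms of 19 and 20, two time points, and a threshold of 0.05 (taken as two-sided). Everything else below is an assumption and is labelled so.

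**1. Which named test covers the randomised comparison?**

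| Test | Assigned to | Compares arms on pre/post scales? |
|---|---|---|
| Two-way ANOVA, interaction | pre/post scales | Yes (parametric) |
| Mann-Whitney U | sociodemographic factors | Not as assigned |
| Wilcoxon signed-rank | Interact scores, BLT arm only | No |
| Friedman | weekly mood and behavior scores, BLT arm only | No |

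The non-parametric branch is empty for this comparison.

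**2. What the interaction tests.** Let d be post minus pre, with arm means d1 and d0 and pooled SD s. The interaction mean square is (d1 − d0)² / [2(1/19 + 1/20)] and the error mean square is s²/2. Hence F = (d1 − d0)² / [s²(1/19 + 1/20)] = t², with 1 and 19 + 20 − 2 = 37 degrees of freedom. In one simulated data set both sides were 0.00875. Normality matters for d within arms, not for raw scores.

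**3. How often raw scores fail Shapiro-Wilk at n=39 (assumed shapes).**

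- Lognormal, sigma 0.3 to 0.5: about 45% to 84%. In a single arm of 19 or 20: about 23% to 52%.
- Gamma with shape 2: about 87% (pre score).
- Rounded scale with a floor at 0: about 99% (pre score).
- Normal: about 5%.

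For the gamma and floor shapes, with latent pre/post correlation 0.7, the change score failed in only about 19-37% of runs.

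**4. Does failing on raw scores show that the interaction test is unsafe?** With 3,000 runs per setting, type I error of the interaction test was 0.047-0.050 (gamma) and 0.044-0.056 (floor), against 0.057-0.061 for normal data. The simulation error is about √(0.05 × 0.95 / 3,000) = 0.004. The rule would send most such scales away from a test that worked.

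**5. Hypothetical: the gap filled by within-arm tests.** Assume both arms truly change by the same amount, in units of the SD of change. Power of a one-sample t test (noncentral t), and the chance that BLT alone is significant:

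- 0.3 SD: power 0.236 (n=19) and 0.247 (n=20). BLT alone: 0.236 × (1 − 0.247) = 0.18.
- 0.5 SD: power 0.541 and 0.565. BLT alone: 0.541 × (1 − 0.565) = 0.24.
- 0.6 SD: power 0.696 and 0.721. BLT alone: 0.696 × (1 − 0.721) = 0.19.

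The range is about 18-24%, with no true difference between arms.

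**6. What baseline adjustment offers.** With equal SD at both visits and correlation ρ, the error variance is proportional to 2(1 − ρ) for change and 1 − ρ² for the baseline-adjusted post score. The ratio is (1 + ρ)/2: 0.75 at ρ = 0.5 and 0.85 at ρ = 0.7. For an assumed effect of 0.6 SD of the raw score, simulated power rose from 0.44 to 0.54 (ρ = 0.5) and from 0.66 to 0.71 (ρ = 0.7).

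**The case against.** The strongest reply is that the SAP says plainly, without condition, that group differences are tested by the interaction. A reader might infer from the selection rule that the plan gives up the randomised comparison for non-normal scales. The text does not say that. What stands is a conflict between the rule and the ANOVA sentences, with no statement of which prevails.

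A reader might also infer that within-arm Wilcoxon tests are planned for the pre/post scales. They are not. The SAP assigns that test to Interact scores, which have no control arm, so the 18-24% figure describes one way of filling the gap and not a planned analysis.

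It could be said that a suitable rank test is already in the document. In part that is right: by the identity above, Mann-Whitney on change scores is a direct rank counterpart of the interaction, and its simulated type I error was 0.046-0.058. But the SAP assigns it only to sociodemographic factors.

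Nor does choosing a test from the data by itself inflate error much. Switching between the interaction and Mann-Whitney on change, according to Shapiro-Wilk on raw scores, held error at 0.046-0.061. The switch did affect power for the floored shape at a 0.5 SD effect (0.355 after switching against 0.441 for the interaction), and helped for the gamma shape (0.553 against 0.497).

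Finally, the point does not reach every analysis. The Friedman test and the paired t test for physiological parameters are given without restating the rule.

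**Conclusion.** The point holds for the pre/post scales. The stated rule selects tests on the raw variable, its non-parametric branch contains no between-group test for these outcomes, and the unconditional ANOVA sentences contradict it. The main harm is the undefined randomised comparison, open to a choice after the data are seen; the two-stage selection as such is secondary.

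The text alone establishes the gap, the conflict and the wrong criterion. How many scales are affected depends on the assumed shapes: few if scores are near normal, roughly half to nearly all if they are skewed or floored as in the settings tried. The false-positive figure holds only if within-arm tests were used to judge treatment, and only for an equal true change of 0.3-0.6 SD of change. It should be quoted with both conditions.

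**What to change.** In Data management and statistical analysis:

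1. Delete the normality rule for the pre/post outcomes.
2. Pre-specify one between-group analysis for every such scale: the post score compared between arms, adjusted for the baseline score and the cognitive-status stratum used at randomisation, with assumptions checked on the residuals.
3. Name a rank or permutation test on change scores as a sensitivity analysis, reported whatever the residuals show.
4. State that within-arm tests are not used to judge the treatment effect.

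Keeping the interaction and merely removing the rule would also close the gap. The adjusted comparison is preferred because it uses the same data with smaller error variance and reflects the stratified randomisation.

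The cost is a few sentences and a short script in the R software already listed. The stratum uses one degree of freedom for each level beyond the first, and the levels, which this SAP does not spell out, must be written down. A permutation test that respects the strata needs the same definition.
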